8.1.1 PATIENT CHARACTERISTICS

The following characteristics will be reported for all treatment cohorts at baseline.

- Demographic Characteristics: Age, BMI, Smoking

Age (years) at index date will be calculated as Age = year (index date)-year (birth).

Four age groups are defined (in years): 45-49, 50-59, 60-69 and 70 and over.

BMI (Body Mass Index) will be calculated for each patient as the weight in kg divided by square of height in meters. BMI will be calculated using the following formulas:

$$BMI (kg/m^2) = Weight (kg) / (Height (m))^2$$

Or

$$BMI (kg/m^2) = 10000 \times Weight (kg) / (Height (cm))^2$$

- BMI will be categorized into four groups as follows:
- Underweight: BMI <18.5 kg/m²
 - Normal range: 18.5 ≤ BMI <25 kg/m²
 - Overweight: 25 ≤ BMI <30 kg/m²
 - Obese : BMI ≥30 kg/m²
- Smoking will be defined as three categories; Current Smokers, Former Smokers and Never Smokers. A 'Current Smoker' will be defined as a patient who is currently smoking at the index prescription date, a 'Former Smoker' as a patient that has a past history of smoking but has stopped prior to the index prescription date. A 'Never Smoker' will be defined as a patient that has no history of smoking (The reported frequency of smoking may be very low because smoking status is under recorded in Italian and Spain databases)
 - Alcohol use. Alcohol use will be defined as three categories; Current Drinkers, Former Drinkers and Never Drinkers. A 'Current Drinker' will be defined as a patient who is currently drinking alcohol as at the index prescription date, a 'Former Smoker' as a patient that has a past history of drinking alcohol but has stopped drinking prior to the index prescription date. A 'Never Drinker' will be defined as a patient that has no history of drinking alcohol. (The reported frequency of alcohol use may be very low because alcohol use is under recorded in Italian and Spain databases).
 - Use of relevant concomitant medications, e.g., hormone replacement therapy. (A concomitant medication is any medication used during BZA/bisphosphonate/raloxifene treatment defined as the total treatment duration between the first and the last prescription of BZA/bisphosphonate/raloxifene.)
 - Medical History VTE (Venous Thromboembolic Events), Diabetes, Hypertension, and Malignancies (including Breast, Renal, Thyroid, Ovarian, Gastrointestinal tract, Lung) and aggregate of all malignancies.

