- Previous history of major lower extremity (hip, knee) arthroplasty, arthroscopic surgery (information on arthroscopic surgery not available in Italian database)
- General surgery, major orthopedic surgery (<1month prior to incidence of VTE)
- (Information on general surgery not available in Italian database)
- Multiple trauma (<1month prior to incidence of VTE)
- Hip, pelvis, or leg fracture (<1month prior to incidence of VTE)
- Stroke (<1month prior to incidence of VTE)
- Acute spinal cord injury (paralysis) (<1month prior to incidence of VTE)
- Hormone replacement therapy (limited information available in both databases)

A Cox model will be used in order to take into account the time varying component. The time from the beginning of the treatment (one among three types, BZA, raloxifene, and bisphosphonate) to the occurrence of primary end point is fitted in this model. The Proportional Hazards (PH) assumption will be tested for each covariable. If the PH assumption does not hold for some covariates, the use of time-varying HR for those covariates will be explored. If a categorical variable with more than 2 levels does not satisfy this PH assumption, collapsing some categories will be attempted to satisfy the PH assumption. Correlations between variables will also be evaluated in order to find independent factors and a final model that is clinically relevant.

First, the univariate analysis will be carried out on each covariable in order to determine the explanatory variables to be included in the final multivariate model. All significant variables with a p -value ≤ 0.20 in the univariate model will be taken into account in the multivariate Cox model.

If > 80% of the important risk factors for VTE listed above does not satisfy the PH assumption, a logistic regression analysis would be performed instead of Cox model to otherwise determine if the covariable is related to the incidence primary endpoint (VTE). The dependent variable would be the incidence of the primary end point during the follow-up period categorized as a binary variable. The 2 indicators of treatment group (BZA vs. bisphosphonates, raloxifene, will be forced in the multivariate model (Cox model or logistic model) to analyze incidence in each class of treatment, adjusted on

significant factors. Hazard ratios (HR) (odds ratios (OR) in case of logistic regression) with 95% Confidence intervals (CIs) and p-values will be presented.

[figure not shown]
Patients Switching Medications

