8.2 STATISTICAL ANALYSES

8.2.1 PATIENT CHARACTERISTICS

Descriptive statistics on available patient characteristics (e.g. age, BMI, smoking, history of relevant medical diagnoses) will be reported for all exposure groups at index date. A summary table will present and compare all the patients' demographic data at index date (BZA/raloxifene/bisphosphonates).

- Age (years): derived by difference between the year of time of interest and year of birth.
- Weight (kg): recorded at the given date, or if not available, at the most recent date before or it
- Height (cm): the value at the given date or, if not available, at the most recent date before or after it.

- Body Mass Index (BMI) (kg/m^2), calculated from weight and height as defined previously. BMI will be described in quantitative measure and in categorical data, as usual
- Alcohol use
- Smoking status
- Time since diagnosis of osteoporosis: derived by the difference between the index date and the diagnosis date.
- Previous treatment for osteoporosis (before index date) (yes versus no) or Number of different treatments for osteoporosis in the entire patient history available
- Previous history of VTE (Venous Thromboembolic Events) (before index date)
- Previous history of major lower extremity (hip, knee) arthroplasty, arthroscopic surgery (information on arthroscopic surgery not available in Italian database)
- General surgery, major orthopedic surgery (<1month prior to incidence of VTE) (information on general surgery not available in Italian database)
- Multiple trauma, (<1month prior to incidence of VTE)
- Hip, pelvis, or leg fracture (<1month prior to incidence of VTE)
- Stroke (<1month prior to incidence of VTE)
- Acute spinal cord injury (paralysis) (<1month prior to incidence of VTE)
- Hormone replacement therapy (limited information available in both databases)

If the diagnoses for any of the conditions listed in this section (8.2.1) are not found in the database, they will be assumed to be absent.

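### SAP 8.1.4 allows categories of a confounder to be merged as a remedy for failed proportional hazards, with no priority for time-varying terms and no check against the unmerged model, so adjustment of the treatment HR may be weakened

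*SAP*

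**What the plan says.** SAP 8.1.4 states that "The Proportional Hazards (PH) assumption will be tested for each covariable". For covariates that fail, "the use of time-varying HR for those covariates will be explored". The next sentence adds a second remedy for categorical variables with more than two levels: "collapsing some categories will be attempted to satisfy the PH assumption". A third provision applies only at the extreme: "If > 80% of the important risk factors for VTE listed above does not satisfy the PH assumption", logistic regression replaces the Cox model.

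The SAP names no PH test or threshold. It does not say whether time-varying terms or merging comes first, which variables may not be merged, or whether the unmerged model is also reported. It does not mention a stratified Cox model.

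The merging sentence names no variable. SAP 8.1.1 says "Four age groups are defined (in years): 45-49, 50-59, 60-69 and 70 and over" and "BMI will be categorized into four groups as follows", and gives smoking three categories. These definitions belong to the description of patients. SAP 8.1.4 lists age and BMI as candidate factors without a form, and SAP 8.2.1 says "BMI will be described in quantitative measure and in categorical data, as usual".

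SAP 4.2 makes the Cox HR the measure for comparing cohorts on primary and secondary endpoints, although SAP 8.2.4 calls the time-to-event analysis secondary.

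**The concern.** Age, BMI and smoking are candidates for the model so that imbalances in risk factors between cohorts can be controlled. For that purpose a confounder needs enough detail; its own hazards need not be proportional. Merging levels does not describe an effect that changes over time. It pools women at different risk and leaves the PH test fewer degrees of freedom, so a non-significant result after a merge does not show that the problem is solved. The choice of merge is also made on the outcome data.

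Age control in the HR rests largely on the model. SAP 5.4 draws 10,938 bisphosphonate women so as to keep that group's own age distribution (56.2% aged 70 or over), which does not balance age against bazedoxifene (BZA). The analyses are repeated by country and pooled, in two populations, and under the as-treated and cumulative-risk approaches. Different merges could arise in each, which would make the HRs hard to compare.

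**Working it through.** The plan gives no figure to reproduce on this point, so the check is an illustration.

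**Inputs from SAP 5.4.** 1,823 BZA women; 10,938 sampled bisphosphonate women; bisphosphonate age mix 1.4 / 13.7 / 28.7 / 56.2% in the bands 45-49, 50-59, 60-69 and 70+.

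**Assumed inputs (not in the documents).** VTE rates of 0.6, 0.9, 1.6 and 3.0 per 1,000 patient-years in the four bands; BZA age mix from 3/22/35/40% (mix A) to 5/35/35/25% (mix B); true rate ratio 1; equal person-time per woman.

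**Formula.** Mantel-Haenszel rate ratio = Σ(a·T0/T) / Σ(b·T1/T). Here a and b are expected events in BZA and bisphosphonate women within an age stratum, T1 and T0 their person-time, and T = T1 + T0. A common multiplier on all rates, or on person-time per woman, cancels. Only the relative age gradient and the age mixes matter.

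**Worked case: mix A merged to under 60 against 60+, one year per woman.**
- Under 60, BZA rate: (3×0.6 + 22×0.9)/25 = 0.864. Bisphosphonate rate: (1.4×0.6 + 13.7×0.9)/15.1 = 0.872. Ratio 0.991.
- 60+, BZA rate: (35×1.6 + 40×3.0)/75 = 2.347. Bisphosphonate rate: (28.7×1.6 + 56.2×3.0)/84.9 = 2.527. Ratio 0.929.
- Person-years: 455.75 and 1,651.6 under 60; 1,367.25 and 9,286.4 at 60+.
- Numerator: 0.3938×1,651.6/2,107.4 + 3.2085×9,286.4/10,653.6 = 0.309 + 2.797 = 3.105.
- Denominator: 1.4405×455.75/2,107.4 + 23.464×1,367.25/10,653.6 = 0.312 + 3.011 = 3.323.
- Rate ratio: 3.105/3.323 = 0.935, against a true 1.

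**All merges, true ratio 1:**

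| Age strata used | Mix A | Mix B | BZA mix equal to bisphosphonate |
|---|---|---|---|
| All four bands | 1.00 | 1.00 | 1.00 |
| 45-59 merged, three bands | 0.999 | 0.998 | 1.00 |
| 50-69 merged, three bands | 0.988 | 0.954 | 1.00 |
| Under 70 / 70+ | 0.984 | 0.944 | 1.00 |
| Under 60 / 60+ | 0.935 | 0.883 | 1.00 |

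Under the coarsest merge a true ratio of 1.5 would read 1.5×0.935 = 1.40 to 1.5×0.883 = 1.32.

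**Wider assumptions.** With rates rising 1.5-fold or 2-fold per age band and BZA mixes from 3/22/35/40% to 8/42/33/17%, the ranges are 0.993-0.999 (45-59 merged), 0.916-0.990 (50-69 merged), 0.891-0.986 (under 70 / 70+) and 0.833-0.956 (under 60 / 60+).

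**Does ignoring non-proportionality in age do comparable harm?** Cox models were fitted to simulated cohorts with a non-proportional age effect and true treatment HR 1: 25 runs of 4,000 BZA and 12,000 bisphosphonate women, about 2,000 events each, BZA mix 5/32/36/27%. Mean HRs were 0.996 with four bands, 0.993 with 45-59 merged, 0.948 for under 70 / 70+, and 0.890 for under 60 / 60+ (Monte Carlo standard error about 0.013). In this setting the violation left alone did no detectable harm to the treatment HR, while the coarse merges biased it. The sizes depend on the simulated age effect.

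**The case against.** The strongest reply is that the SAP is better than the merging sentence suggests, and four inferences that a reader might draw go too far.

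- *That merging replaces any real remedy.* The preceding sentence provides for time-varying HRs, for categorical covariates too. What remains is that this is only to be explored, that no priority is set, and that merging is the remedy aimed at multi-level variables.
- *That levels are merged repeatedly until the test passes.* No such loop is written. Merging some categories is to be attempted, and the same paragraph asks for a clinically relevant final model.
- *That age and BMI adjustment will be lost.* Neither is named in the rule. As continuous terms they would escape it. The silence on form stands as a gap.
- *That the rule hides a BZA safety signal.* This needs BZA women to be younger, and the documents do not give their age mix. Protocol section 10 suggests that raloxifene users may be the younger group; if so, under-adjustment would push the BZA-to-raloxifene HR upward.

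The size may also be small. The natural first merge is 45-49 with 50-59, because few events fall in the youngest band, and it costs about 0.1-0.2%. Protocol Table 3 gives an interval of 0.9 to 2.5 for a true ratio of 1.5 at 1:6, wide beside most of these shifts. VTE incidence is also to be stratified by age and BMI, so the rates by band stay visible. These points limit the likely harm. They give no reason to keep a rule that does not model non-proportionality when alternatives that keep full detail are available.

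**Conclusion.** The point holds as a conditional weakness. The SAP permits outcome-driven merging of confounder categories as a PH remedy, does not rank it below time-varying terms, and asks for no comparison with the unmerged model. Residual confounding follows only if a confounder enters in groups, fails the PH test, is merged coarsely, and is distributed differently between cohorts.

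Under the main assumptions, with BZA women younger, the bias at a true ratio of 1 is 0.1-0.2% if only 45-59 is merged, 1-6% for merging 50-69 or for under 70 / 70+, and 6-12% for under 60 / 60+. It is zero if the age mixes match, and the direction reverses if BZA women are older. The BZA age mix and the VTE age gradient are assumptions throughout. This is an inexpensive improvement worth making; it is not a finding that the HR will be biased.

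**What to change.** In SAP 8.1.4, delete the sentence on collapsing categories. State the form in which age and BMI enter the Cox model. Then specify that a categorical covariate that fails the PH test stays at full detail, either as a stratification factor or with a covariate-by-time term, and say which is tried first. The treatment indicators are unchanged.

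The cost is a sentence or two in the SAP and about one line of code. A stratified covariate has no single HR to report, and a little precision is lost.

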In this study the proportion and demographic and clinical characteristics of patients that switch medications between the study drugs will be reported alongside patients that do not switch medications. Both the AT and CR analytic approaches will be used for all study endpoints and the results reported. In the CR method, if a patient switches from one exposure (study drug) cohort group to another, they will have several treatment durations and will belong to multiple cohort groups but will be analyzed according to their original exposure cohort group (i.e., CR/intent to treat approach). In the AT approach, all exposure cohort groups will be included as a time-dependent variable. With the exposure cohort group as a time-dependent variable, each event will be assigned to the treatment being taken at the time of occurrence. The duration of treatment for each cohort group will be from the date of the first prescription to the date of the event or to the end of treatment, whichever occurs first. The covariates of patients that switched treatment at the time of the event or at the end of follow-up would be considered in this model.

[figure not shown]
The following diagrams shows some example of calculating duration for patients with switched treatments with both the AT and CR approaches.

Figure 2a. Calculating the duration of treatment for patients that switched treatment using the as-treated (AT) approach.

A, B, C: Treatment cohort types. X= Incidence date of primary end point

Figure 2b. Calculating the duration of treatment for patients that switched treatments using the cumulative risk (CR) approach.

A, B, C: Treatment cohort types. X= Incidence date of primary end point

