8.2.4 TIME TO EVENT ANALYSIS

Time to event analysis will be conducted as a secondary analysis and the following factors possibly related to incidence of end points will be considered at the date of Incidence or the last visit before incidence: age, BMI, smoking (depending on availability of data), history of diabetes, history of hypertension, history of malignancies, history of VTE, and some other co-morbidities. Univariate Cox models (if applicable, depending on the PH assumptions for each factor, otherwise logistic regression model) will be performed for each factor and then, the analysis will be complemented by a multivariate Cox model (if applicable, depending on the PH assumptions for each factor) or a logistic regression. Hazard ratios (HR) or odds-ratios with 95% CI and p-values will be presented for significant factors at the 0.05 level.

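### The SAP gives two conflicting rules for replacing the Cox model with logistic regression, and the logistic model it specifies ignores unequal follow-up and cannot hold time-dependent exposure

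*SAP*

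**What the plan says.** SAP 8.1.4 tests PH for each covariate. For those that fail, "the use of time-varying HR for those covariates will be explored", and categorical variables may have levels merged. The switch comes only after that: "If > 80% of the important risk factors for VTE listed above does not satisfy the PH assumption", then "a logistic regression analysis would be performed instead of Cox model". The logistic outcome is defined as follows: "The dependent variable would be the incidence of the primary end point during the follow-up period categorized as a binary variable". No follow-up term or offset is given, and the result is reported as an odds ratio.

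SAP 8.2.4 describes the same analysis under the same title. The univariate Cox models apply "if applicable, depending on the PH assumptions for each factor, otherwise logistic regression model". The adjusted analysis is a "multivariate Cox model (if applicable, depending on the PH assumptions for each factor) or a logistic regression". This section mentions neither the 80% threshold nor time-varying HRs.

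Three other parts of the SAP bear on the point:
- **Comparison measure.** Sections 4.1, 4.2 and 8.2.2 state the hypotheses and the comparison as a Cox HR.
- **Follow-up.** Under sections 2.1 and 8.1.2 it ends at the event, the last visit or five years, so its length differs between women. Deaths are not recorded in either database.
- **As-treated (AT) analysis.** Under the switching rules in 8.1.4, "In the AT approach, all exposure cohort groups will be included as a time-dependent variable".

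**The concern.** The two sections allow different models for the same data, and the choice would be made after the PH tests have been seen. An analyst could follow either section and be within the plan.

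The fallback is also a poor substitute whichever rule applies. A woman last seen event-free at six months counts the same as a woman event-free for five years. If loss to follow-up differs between cohorts, that difference enters the odds ratio as though it were a drug effect, or offsets a real one. One record per woman with one outcome also has no place for an exposure that changes over time.

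Non-proportional covariates are not a reason to discard follow-up time when estimating the drug effect. A Cox model can be stratified on such a covariate or given a time interaction, and 8.1.4 already names time-varying HRs. The switch would change the measure from a hazard ratio to an odds ratio that depends on follow-up, for the covariate-adjusted comparison that the SAP otherwise bases on person-time.

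**Working it through.** The documents give no figure for this rule, so there is none to reproduce. Two checks were made.

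**1. How easily does each rule trigger?**

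The list in 8.1.4, leaving out treatment, has 14 factors, or 16 if diabetes, hypertension and malignancies are counted separately. The SAP sets no level for the PH test. I assume 0.05 per test, independent tests, and PH true for every factor.

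- Rule in 8.1.4: more than 80% must fail. 0.8 × 14 = 11.2, so at least 12 of 14; 0.8 × 16 = 12.8, so at least 13 of 16. The binomial tail probabilities are about 2 × 10⁻¹⁴ and 6 × 10⁻¹⁵. Even if each factor failed half the time, they would be only 0.6% and 1.1%.
- Rule in 8.2.4, on the strictest reading (one failure is enough): 1 − 0.95¹⁴ = 0.51 and 1 − 0.95¹⁶ = 0.56.

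These figures show how far apart the two rules can be. They do not predict what will happen, because the level, the independence and the strict reading are all assumed.

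**2. What does the binary model return when follow-up differs?**

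Inputs: comparator VTE rate r = 1.74 per 1,000 person-years and loss of 15% a year, both from protocol 7.1, and a five-year cap. Bazedoxifene loss is assumed, from 5% to 30% a year, because no document gives loss by cohort. Hazards are taken as constant.

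With annual loss l, the loss hazard is d = −ln(1 − l). The chance of an observed event is

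risk = [rate/(rate + d)] × [1 − exp(−5(rate + d))],

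with rate = r for the comparator and rate = HR × r for bazedoxifene. The odds ratio (OR) follows from the two risks.

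| Bazedoxifene loss per year (assumed) | OR at true HR 1 | OR at true HR 2 |
|---|---|---|
| 5% | 1.29 | 2.59 |
| 10% | 1.14 | 2.28 |
| 15% (equal to comparator) | 1.00 | 2.00 |
| 20% | 0.88 | 1.76 |
| 25% | 0.77 | 1.55 |
| 30% | 0.68 | 1.36 |

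A simpler calculation confirms this. For a rare event the OR is close to HR × the ratio of mean person-years, where mean person-years = (1 − (1 − l)⁵)/(−ln(1 − l)). This gives 3.42 at 15%, 3.01 at 20% and 2.65 at 25%. Then 3.01/3.42 = 0.88 and 2.65/3.42 = 0.77, as in the table. A person-time method would return the true ratio in every row.

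**Expected bazedoxifene events**, which matter for the fix: 1,823 women (SAP 5.4) × 3.42 person-years × 1.74/1,000 ≈ 11 at a ratio of 1, and about 22 at a ratio of 2.

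**The case against.** The strongest reply is that 8.1.4 holds the full rule and 8.2 only restates 8.1, so the PH condition in 8.2.4 can be read as pointing back to the 80% threshold. On that reading the fallback is almost unreachable. This is a fair reading, but the SAP does not state it, and the wording of 8.2.4 does not require it.

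A reader might infer that one failed PH test would move the whole treatment comparison to logistic regression. The documents do not establish that. In the univariate clause, a failing factor changes the screening model for that factor. The adjusted clause is ambiguous, and only its strictest reading gives the single-failure trigger. The number of usable tests is also uncertain: smoking may be dropped if poorly recorded, and history of DVT or PE should not vary in the primary VTE analysis, which excludes women with prior VTE.

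Other outputs limit the damage. Person-time incidence rates and rate ratios are planned (8.1.2), numbers lost to follow-up will be reported (2.1), sections 4.2, 8.2.2 and 8.2.5 name Cox with no logistic alternative, and 8.2.4 calls the time-to-event analysis secondary. An imbalance in loss would therefore be visible, but the adjusted ratio could still be the wrong one.

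Finally, logistic regression on person-period records can hold time-dependent exposure. That is correct, but 8.1.4 specifies a single binary outcome over follow-up. Nothing says that the fallback would displace the AT analysis; it simply could not be used for it.

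**Conclusion.** The point stands as a conflict between two sections together with an unsuitable fallback. SAP 8.1.4 and 8.2.4 give different conditions for leaving the Cox model, and neither is said to govern. The logistic model as specified ignores unequal follow-up and cannot carry the AT exposure.

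The size is conditional. With equal loss and a rare event the odds ratio is close to the hazard ratio and there is little harm. With comparator loss of 15% a year and assumed bazedoxifene loss between 5% and 25%, a true HR of 1 gives an OR from 1.29 down to 0.77, and a true HR of 2 gives from 2.59 down to 1.55. A reader might infer that the fallback would hide a VTE risk. The documents do not support a direction, because they do not report loss by cohort and the error can go either way.

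**What to change.** 1. Reconcile 8.1.4 and 8.2.4 so that one rule governs, and delete the logistic fallback from both.
2. If a covariate fails the PH check, stratify on it or add its interaction with time. State how PH will be tested and at what level.
3. If the Cox model cannot be fitted, use Poisson regression with a log person-time offset. Splitting follow-up by exposure period lets it hold the AT exposure too.
4. If the treatment term itself fails PH, period-specific HRs may be reported, but descriptively: about 11 to 22 bazedoxifene events leave few in each period.

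The cost is a change of SAP wording. No new data are needed, and the remedy extends one that 8.1.4 already names.
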